2.3 Rationale for Dose Selection

Nivolumab is safe and well tolerated up to 10 mg/kg Q2W dose level (see IB). The RT given in the present study gives considerable side effects, related to inflammation that may be enhanced by PD1 blockade. Nivolumab has shown efficacy and mild toxicity when given as monotherapy for HNSCC at a dose of 3.0 mg/kg Q2W, which is the target dose in the present trial(3). To assess the toxicity, the following dosing schedule has been chosen: Nivolumab, intravenous every 2nd week (1 cycle = 2 weeks), dose escalation schedule (1.0, 3.0 mg/kg), for a maximum of 12 months or until disease progression. RT will be given to a total dose of 60 Gy (1.5 Gy fractions twice daily) for a total period of 4 weeks. We expect that any increased toxicity will be observed within 2 weeks after end of RT and thus allow for a 3.0 mg/kg Q2W dose level thereafter. If a drug-related toxicity is observed, the guidelines outlined below will apply.

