3.0 SAFETY MONITORING COMMITTEE

A safety monitoring committee (SMC) will monitor safety on a periodic basis. Members of the

SMC will be experienced clinicians. The SMC will meet approximately every 6 months from the point of first patient in (FPI) to review safety and study conduct data. The safety data will include demographic data, adverse events and relevant laboratory data. In addition the SMC will meet after finalization of each dose cohort (i.e. three patients has completed minimum 8 weeks of treatment), and in case DLT is experienced. See section 8.8 for definitions.

Following each data review, the SMC will provide recommendations to the Study Leadership as to whether the study should continue or be amended, or whether the study should be stopped on the basis of safety (i.e., evidence of harm). The Study Leadership will make a decision on the basis of the SMC recommendations.

Any outcomes of these safety reviews that affect study conduct will be communicated in a timely manner to the investigators for notification of the Institutional Review Boards/Ethics Committees (IRBs/ECs).

No interim efficacy analysis is planned.

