5.2 Study treatment

The study will include 20 patients. The following treatment will be used:

- Radiotherapy (RT) to a total dose of 60 Gy, given as 1.5 Gy fractions twice daily for a total period of 4 weeks, will be delivered to the target volumes determined by PET-CT scan. Definition of target volumes and organs at risk will follow the Dahanca guidelines 2013 (published on www.dahanca.dk). The dose delivered to organs at risk, determined by PET-CT scan, will also be calculated.
- Nivolumab administered intravenous every two weeks, starting two weeks (Cycle 1, Day 1) before start of radiotherapy. Nivolumab will be given for a maximum of 12 months or until disease progression.
- Nivolumab will be administered according to a dose escalation schedule (1.0 and 3.0 mg/kg), as shown in Figure 1. Three patients will be included at each dose level. During the dose escalation part the subsequent patient will start therapy with nivolumab 6 weeks after the previous to allow time to observe the possibility for acute toxicity. If no dose limiting toxicity (DLT) is observed at the first dose level, additional three patients will be included at the next dose level. If DLT is experienced see section 8.8 for details. The remaining patients will be treated at the maximum tolerated dose.
- The nivolumab dose will be adjusted to 3.0 mg/kg (standard dose used in NCT02105636) for all patients from Cycle 5, Day 1 (2 weeks after end of radiotherapy), irrespective of starting dose.

The study treatment is outlined in Table 1. Trial treatment should begin within 28 days of first interventional screening assessments. Details on preparation and administration of nivolumab are provided in the IB.

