5.2.1 Study drug

The product storage manager at the local pharmacy should ensure that the study drug is stored in accordance with the environmental conditions (temperature, light, and humidity) as determined by BMS. If concerns regarding the quality or appearance of the study drug arise, the study drug should not be dispensed and contact BMS immediately.

Investigational product documentation must be maintained. That includes all processes required to ensure drug is accurately administered. This includes documentation of drug storage,

administration and, as applicable, storage temperatures, reconstitution, and use of required processes (eg, required diluents, administration sets).

Infusion-related supplies (eg, IV bags, in-line filters, 0.9% sodium chloride injection, 5% dextrose injection) will not be supplied by the sponsor and should be purchased locally if permitted by local regulations.

The investigational product should be stored in a secure area according to local regulations. It is the responsibility of the investigator to ensure that investigational product is only dispensed to study subjects. The investigational product must be dispensed only from official study sites by authorized personnel according to local regulations.

[figure not shown]
Please refer to the current version of the Investigator Brochure (IB) and/or pharmacy reference sheets for complete storage, handling, dispensing, and infusion information for nivolumab.

The infusion will be administered by nurses with experience in treatment with immunotherapy.

Table 1 Study Treatment

Drug	Dose/Potency	Dose Frequency	Route of Administration	Regimen/Treatment Period	Use
Nivolumab	1,0 mg/kg	Q2W	IV infusion	Day 1 of each 2 week cycle	Experimental, Dose level 1
Nivolumab	3,0 mg/kg	Q2W	IV infusion	Day 1 of each 2 week cycle	Experimental, Dose level 2
Radiotherapy	1,5 Gy	BID		5 days a week, 4 weeks (Cycle 2 and 3)	Standard

Figure 1

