9.8 Dose Limited Toxicity (DLT)

We foresee that DLT related to Grade 3 and/or 4 dermatitis and mucositis may be experienced.

During dose escalation phase: If a patient experience a possibly nivolumab-related Grade 3 adverse event at any dose level, an additional patient will be included at this dose level. If one more patient experience the same Grade 3 event on the same dose level (i.e. 2 of 4 patients at one dose level experiences the same Grade 3 event), this will be defined as DLT reached, and the dose should be reduced by one level. If DLT is experienced at the lowest dose level (1,0 mg/kg), the dose will be reduced to 0.3 mg/kg. If two patients experience DLT at this dose level, the study will be terminated. If a patient experiences a Grade 4 event, the dose should immediately be reduced by one level.

The Safety Monitoring Committee (SMC) will meet in the case of DLT, to discuss further progress related to doses of nivolumab, and whether the protocol should be amended. In

addition, the SMC will meet after every time three patients have completed each dose level (i.e. completed the re-radiation), to discuss whether it will be safe to move to next dose level. No further patients will be included until the SMC has met. After the dose escalation phase has been completed, the SMC will meet if two patients experience AE grade 3 or one patient experiences AE Grade 4, considered related to nivolumab. No further patients will be included until the SMC has met.

The SMC is a group of oncologists located at the Clinical Cancer Research Unit, with experience in immunotherapy treatment. The members will not be involved in the study design or the study treatment.

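### Section 9.8 allows dose-level clearance at the end of re-irradiation, 2 weeks short of the 8 weeks in 3.0, and section 5.2 makes no Cycle 5 exception for a dose reduced under 9.8

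*Combined protocol and SAP*

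**What the plan says.** **Clearance review.** Section 9.8 provides that "the SMC will meet after every time three patients have completed each dose level (i.e. completed the re-radiation", to decide whether moving up a level is safe, and inclusion stops until the committee (SMC) has met. Section 3.0 describes what reads as the same meeting: "the SMC will meet after finalization of each dose cohort (i.e. three patients has completed minimum 8 weeks of treatment". For definitions, 3.0 points to a section 8.8, which the current numbering does not contain; the DLT rules are in 9.8. Both triggers speak of three patients, although 9.8 adds another patient at the level after a possibly related Grade 3 event. No DLT window is stated.

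**Toxicity period.** Section 2.3: "We expect that any increased toxicity will be observed within 2 weeks after end of RT". It uses this expectation to justify 3.0 mg/kg afterwards, and then says that the toxicity guidelines apply if drug-related toxicity is seen.

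**Calendar.** Section 5.2: "Nivolumab administered intravenous every two weeks, starting two weeks (Cycle 1, Day 1) before start of radiotherapy". Table 1 (section 5.2.1) gives radiotherapy as "5 days a week, 4 weeks (Cycle 2 and 3". In escalation, "the subsequent patient will start therapy with nivolumab 6 weeks after the previous" (section 5.2).

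**Dose levels and Cycle 5.** Section 5.2: "Nivolumab will be administered according to a dose escalation schedule (1.0 and 3.0 mg/kg", and "The nivolumab dose will be adjusted to 3.0 mg/kg (standard dose used in NCT02105636) for all patients from Cycle 5, Day 1", whatever dose the patient started on. Section 9.8 adds a 0.3 mg/kg level, used if DLT occurs at 1.0 mg/kg. It says nothing about Cycle 5 after a reduction.

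**The concern.** Primary objective 2 is a safe nivolumab dose given with re-irradiation. The plan itself names the 2 weeks after radiotherapy as part of the period in which added toxicity should appear. If the committee convenes as soon as the last patient finishes radiotherapy, it sees none of those weeks in that patient.

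Longer follow-up of the first two patients does not fully replace them. At the 1.0 mg/kg level everyone moves to 3.0 mg/kg at Cycle 5, so weeks 6 to 8 are the only post-radiotherapy weeks spent on the dose being cleared.

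The Cycle 5 rule raises a separate safety question. Its rationale in 2.3 is that toxicity should have shown itself by then. Once DLT has been reached and the dose lowered, that rationale no longer settles the matter, yet 5.2 read literally still takes everyone to 3.0 mg/kg.

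**Working it through.** **Inputs.** 60 Gy in 1.5 Gy fractions twice daily, 5 days a week (5.2 and Table 1); nivolumab starts 2 weeks before radiotherapy, and starts are 6 weeks apart in escalation (5.2); 2-week cycles (2.3); three patients per level and 20 in total (5.2); enrolment Q2 2017 to Q4 2018 (1.0).

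**The plan's own figure.** Radiotherapy lasts 60 / (1.5 × 2 × 5) = 4 weeks. It starts at week 2 and ends at week 2 + 4 = 6. Cycle 5 Day 1 falls at (5 − 1) × 2 = week 8. The gap is 8 − 6 = 2 weeks, as 5.2 states.

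**Earliest review.** The three patients start at weeks 0, 6 and 12. Under 9.8 alone the review can fall at 12 + 6 = week 18; under 3.0, at 12 + 8 = week 20.

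| | 9.8 alone | 3.0 |
|---|---|---|
| Calendar week of review | 18 | 20 |
| Weeks on study, patients 1, 2, 3 | 18, 12, 6 | 20, 14, 8 |
| Weeks since end of radiotherapy | 12, 6, 0 | 14, 8, 2 |
| Patient-weeks seen of the 8-week period | 8 + 8 + 6 = 22 of 24 | 24 of 24 |
| Post-radiotherapy patient-weeks seen (2 per patient) | 2 + 2 + 0 = 4 of 6 | 6 of 6 |

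The stagger does not close the gap, because it too allows the next start at 12 + 6 = week 18.

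**Who is exposed in the gap.** A next-level patient starting at week 18 begins radiotherapy at 18 + 2 = week 20, which is the last patient's week 8. On nominal dates that patient has had one nivolumab dose and no radiotherapy by then. After the second clearance 20 − 6 = 14 patients remain. Enrolment spans at most seven quarters, about 91 weeks. Two levels use 2 × 18 = 36 to 2 × 20 = 40 weeks, which leaves 51 to 55. Assuming even accrual, the number starting in a 2-week gap is 14 × 2/55 = 0.51 to 14 × 2/51 = 0.55.

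**Fourth patient.** Earliest start 12 + 6 = week 18; radiotherapy ends at 18 + 6 = week 24; week 8 falls at 18 + 8 = week 26.

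**Cycle 5 after a reduction.** For a cohort started at 0.3 mg/kg, 3.0/0.3 = 10 times the starting dose and 3.0/1.0 = 3 times the level where DLT was reached. If four patients had been treated at 1.0 mg/kg, 20 − 4 = 16 would remain to start at 0.3 mg/kg, unless the protocol were amended.

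**The case against.** On timing, the best reply is that 9.8 sets an earliest point and 3.0 a floor, so a site that follows both meets at week 8. That stands. A reader might infer that 9.8 fixes the review at week 6 or that the sections cannot both be met; the text supports neither. What remains is that 9.8, the section a reader consults for DLT rules, permits the earlier meeting when read alone.

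A reader might also infer that clearance exposes 14 of 20 patients to an inadequately reviewed dose. That does not follow: only those starting inside the 2-week gap are affected. After the first clearance the trial is still in escalation, so a late Grade 3 event at 1.0 mg/kg still adds a patient. At 3.0 mg/kg a late event could come under the looser post-escalation rule only if escalation is taken to end at that meeting, which the protocol does not say.

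On Cycle 5, section 2.3 says toxicity guidelines apply, 5.3.2 sends dose modification to the DLT section, and the SMC meets on any DLT and may discuss amendment. It is therefore too strong to say that 5.2 overrides the toxicity rules. Sections 5.3.2.1 to 5.3.2.3 also hold or stop nivolumab for many affected patients, including most related Grade 4 events. But none of these provisions gives a Cycle 5 dose, and the hold and stop rules do not touch an event-free patient in a 0.3 mg/kg cohort. It is also fair that the 10-fold and 3-fold ratios compare a dose during radiotherapy with one after it.

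Finally, one might infer that a patient whose own dose was cut from 3.0 to 1.0 mg/kg returns to the DLT level. A patient may indeed resume after a Grade 3 skin event resolves, but 9.8 does not say whether a reduction covers the affected patient, the cohort or both.

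**Conclusion.** The point holds in limited form and should be fixed. Section 9.8 read alone lets a level be cleared 2 weeks before the period in 2.3 has ended for the last patient, at a cost of 2 of 6 post-radiotherapy patient-weeks. The practical exposure is small. This rests on nominal dates, starts exactly 6 weeks apart, an SMC meeting on the first permitted day and, for the accrual estimate, even enrolment.

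Section 5.2 has no Cycle 5 exception after a reduction under 9.8. The clearest consequence is a 0.3 mg/kg cohort rising to three times the level where DLT was reached. It requires DLT at the lowest planned level and no amendment after the SMC meeting that follows, so it is remote. The planned rise from 1.0 to 3.0 mg/kg in a cohort without DLT is deliberate and is not in question.

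**What to change.** In 9.8, replace the parenthesis that equates a completed dose level with completed re-irradiation. Require instead that all patients at the level, including any added fourth patient, have completed at least 8 weeks, counted up to the Cycle 5 Day 1 dose, and state that this is the DLT window.

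In 5.2, state that the Cycle 5 rise to 3.0 mg/kg does not apply to patients treated at a dose reduced under 9.8 unless the SMC agrees.

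The cost is a few sentences and up to 2 weeks per three-patient cohort (4 weeks over two levels), or none if 3.0 is already followed. With a fourth patient the review falls at week 26: 2 weeks later than waiting for that patient's radiotherapy to end, or 8 weeks later than a week-18 review that does not wait. A reduced cohort may also stay below the 3.0 mg/kg target after radiotherapy until the SMC agrees otherwise; in the 0.3 mg/kg case that is one-tenth of the target. Sample size and the dose-reduction rule do not change.

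### When a Grade 3 event adds a fourth patient to a dose level, no SMC escalation review of that patient is required, so 3.0 mg/kg may open about 2 weeks before the patient's expected toxicity window closes

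*Combined protocol and SAP*

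**What the plan says.** Section 9.8 has the SMC meet on a count of three: "the SMC will meet after every time three patients have completed each dose level", where completing a level means completing re-irradiation. The purpose is "to discuss whether it will be safe to move to next dose level", and recruitment is held meanwhile: "No further patients will be included until the SMC has met". Section 3.0 sets a later point but the same count: "In addition the SMC will meet after finalization of each dose cohort (i.e. three patients has completed minimum 8 weeks of treatment".

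The decision rule in 9.8 goes beyond three. One possibly nivolumab-related Grade 3 event adds a patient at that level, and DLT is reached if "2 of 4 patients at one dose level experiences the same Grade 3 event". A Grade 4 event acts at once: "If a patient experiences a Grade 4 event, the dose should immediately be reduced by one level".

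Section 5.2 spaces starts 6 weeks apart during escalation and opens the next level if no DLT has been observed. It states no observation period for that condition. It also moves every patient to 3.0 mg/kg from Cycle 5 Day 1. Section 2.3 expects any added toxicity to show within 2 weeks after radiotherapy. Section 3.0 also provides for general SMC meetings about every 6 months.

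**The concern.** The stopping rule was extended to a fourth patient and the review was not. Patient 4 is enrolled because toxicity was seen, so this patient's course is the most informative evidence on whether the level is safe. The three-patient review takes place when patient 4 has little or no follow-up. Once that meeting has been held, the recruitment hold is satisfied and no further escalation review is required unless DLT is declared.

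What is new at the higher level is 3.0 mg/kg before and around radiotherapy (Cycles 1 to 4), because everyone receives 3.0 mg/kg from Cycle 5. That is the exposure the second primary objective concerns, and it could begin before patient 4 has passed the window in which the protocol itself expects trouble.

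**Working it through.** **Inputs**
- Nivolumab starts 2 weeks before radiotherapy (5.2).
- Radiotherapy is 60 Gy in 1.5 Gy fractions, twice daily, 5 days a week (5.2, Table 1).
- Added toxicity is expected until 2 weeks after radiotherapy (2.3).
- Starts are 6 weeks apart (5.2).
- The review falls when the third patient ends radiotherapy (9.8) or reaches 8 weeks (3.0).

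**Weeks from a patient's first dose.** Fractions: 60 / 1.5 = 40. Duration: 40 / (2 × 5) = 4 weeks. Radiotherapy ends at 2 + 4 = week 6 and the window closes at 6 + 2 = week 8. Cycle 5 Day 1 is (5 − 1) × 2 = week 8. This reproduces the 8-week minimum in section 3.0.

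**Study calendar, earliest permitted dates.** Patients 1 to 3 start at weeks 0, 6 and 12. Patient 3 ends radiotherapy at 12 + 6 = 18 and reaches 8 weeks at 12 + 8 = 20.

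| | A: 9.8 review | B: 3.0 review, patient 4 not held | C: 3.0 review, patient 4 held |
|---|---|---|---|
| Three-patient review | 18 | 20 | 20 |
| Patient 4 starts | 18 | 18 | 20 |
| Patient 4 data at review (weeks) | 0 | 2, before radiotherapy | 0 |
| First 3.0 mg/kg start (patient 4 + 6) | 24 | 24 | 26 |
| Patient 4 window closes (patient 4 + 8) | 26 | 26 | 28 |
| Shortfall (weeks) | 2 | 2 | 2 |

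The second higher-dose start is 6 weeks after the first, at week 30 (A, B) or 32 (C). Patient 4 is then at week 12, so only one patient can start early.

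**Other SMC meetings**
- The 6-monthly meeting falls at week 26 if first patient in means first dose. Patient 4 is then at week 8 (A, B) or 6 (C). If it is counted from screening up to 4 weeks earlier (an assumption), it falls at week 22, with patient 4 at week 4 or 2. It is not an escalation review and need not come before the first higher-dose start.
- Section 9.8 also uses DLT for individuals ("If two patients experience DLT at this dose level"). On that reading the SMC would meet at the first Grade 3 event, which is again before patient 4 has any data.

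**Dose already given.** When patient 4's window closes, the higher-dose patient has had one 3.0 mg/kg dose and is due Cycle 2 and radiotherapy. Section 5.1.1 gives a half-life of up to 25 days. With simple exponential decline assumed, 2^(−14/25) = 0.678 of the dose remains after 14 days, and 0.678 × 3.0 = 2.03 mg/kg. For an assumed half-life of 15 days, 2^(−14/15) = 0.524, and 0.524 × 3.0 = 1.57 mg/kg.

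**How often patient 4 decides DLT.** The documents give no event rate. With an assumed per-patient probability p of the same Grade 3 event, the chance of exactly one event in the first three and then one in patient 4 is 3p(1 − p)² × p. This is 2.4% at p = 0.1, 7.7% at 0.2, 13.2% at 0.3 and 17.3% at 0.4. These figures cover an event at any time, so they overstate the chance of one confined to weeks 6 to 8.

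**The case against.** **Week 8 is not the escalation standard.** Section 9.8 counts a level as complete at the end of radiotherapy, week 6, which patient 4 has reached. Section 2.3 is a rationale for the Cycle 5 step-up, not a stated DLT window. Under 9.8 alone the same 2-week gap exists for patient 3 in a clean cohort. This partly stands, since the two sections do differ. But section 3.0 sets 8 weeks for cohort review, and that closes the gap for patient 3. It does not close it for patient 4 (case C).

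**The SMC can wait.** The three-patient meeting knows of the Grade 3 event and may recommend deferral. That is true, but deferral is discretionary and no second review is required afterwards. The reference to finalizing a cohort in 3.0 could be stretched to include patient 4, but its own gloss fixes the number at three.

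**A second review adds little.** A matching Grade 3 event in patient 4 already triggers the DLT rule, and without one the SMC sees 1 of 4. This overlooks a different Grade 3 event in patient 4. Such an event would not meet the same-event rule and, unless DLT is read as a single-patient event, would prompt no meeting.

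**The harm needs a chain of events.** It requires meetings without lag, starts on the earliest dates, no deferral, and an event first appearing in weeks 6 to 8. This stands as to likelihood: a 2-week slip in the higher-dose start removes the gap.

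**The residual dose needs a comparator.** On the 25-day model, a 1.0 mg/kg patient carries 1.0 + 0.68 = 1.68 mg/kg after the Cycle 2 dose. If the higher-dose patient's Cycle 2 is withheld, the contrast is only 2.03 against 1.68. Section 5.3.2.1 would allow such a delay at the investigator's judgment. But reduction by one level, which is what the plan prescribes, gives 2.03 + 1.0 = 3.03 against 1.68. The 68% is an upper figure, since a terminal half-life ignores any faster early decline. Section 2.3 also describes 3.0 mg/kg monotherapy toxicity as mild, although it warns that PD-1 blockade may enhance radiotherapy inflammation.

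**Conclusion.** The concern holds. Followed exactly, the three-patient trigger lets 3.0 mg/kg open with patient 4 at week 6 of the 8 weeks in which the protocol expects added toxicity, and with no SMC look at the four-patient data required. The 2-week shortfall appears under all three readings of the review timing. It is the earliest-date case and assumes that starts follow the 6-week stagger without slippage.

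The consequence is limited to about one patient and one pre-radiotherapy dose, of which up to 68% (about 2.0 mg/kg) may remain when that patient's radiotherapy starts. It arises only after a Grade 3 event, and the DLT and Grade 4 rules continue to act. This is a point for the sponsor to consider, with medium confidence, and not a fundamental flaw in the design.

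**What to change.** Keep the three-completer review and its recruitment hold, so that the SMC sees the 1-of-3 data before patient 4 is dosed. Add to sections 3.0 and 9.8 that a level expanded after a Grade 3 event is not cleared, and that no patient starts at the next level, until a second SMC review. Hold that review after the added patient has completed at least 8 weeks, that is, 2 weeks after the end of radiotherapy.

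The cost is wording in two sections and, only after a Grade 3 event, one extra SMC meeting. The earliest higher-dose start moves from week 24 to 26, or from week 26 to 28 if patient 4 is held until the week-20 review, plus the time to convene the meeting. No patients are needed beyond the planned 20.

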 - Dosing delays to allow for prolonged steroid tapers to manage drug-related adverse events are allowed.
 - Dosing delays lasting > 6 weeks from the previous dose that occur for non-drug-related reasons may be allowed, if approved by the Study leadership.

- Prior to re-initiating treatment in a subject with a dosing delay lasting > 6 weeks, the Study leadership must be consulted. Tumor assessments should continue as per protocol even if dosing is delayed. Periodic study visits to assess safety and laboratory studies should also continue every 6 weeks or more frequently if clinically indicated during such dosing delays.
- Any adverse event, laboratory abnormality, or intercurrent illness which, in the judgment of the Investigator, presents a substantial clinical risk to the subject with continued nivolumab dosing.

For detailed information see the IB for nivolumab.

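### Sections 3.0 and 9.8 time the same escalation review differently, and under 9.8 it can take place before the third patient has any observation after radiotherapy

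*Combined protocol and SAP*

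**What the plan says.** Two sections define when a dose level is complete for SMC review.

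- Section 3.0 has the SMC meet after "finalization of each dose cohort (i.e. three patients has completed minimum 8 weeks of treatment".
- Section 9.8 has it meet after "three patients have completed each dose level (i.e. completed the re-radiation), to discuss whether it will be safe to move to next dose level". It also holds inclusion until the meeting has taken place, and states no minimum observation time after RT.

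Three other statements fix the calendar.

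- Section 2.3: "We expect that any increased toxicity will be observed within 2 weeks after end of RT".
- Section 5.2 moves the nivolumab dose to 3.0 mg/kg "for all patients from Cycle 5, Day 1 (2 weeks after end of radiotherapy), irrespective of starting dose".
- Section 5.2, for the escalation part: "the subsequent patient will start therapy with nivolumab 6 weeks after the previous".

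Section 5.2 also gives the escalation step itself, without an observation time: "If no dose limiting toxicity (DLT) is observed at the first dose level, additional three patients will be included at the next dose level". Section 3.0 sends the reader to section 8.8 for definitions. No section 8.8 exists in the current numbering; the dose-limiting toxicity text is 9.8.

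**The concern.** Both sections describe the SMC review that closes a dose level, and each gives its own definition of completion. They differ by 2 weeks, and those 2 weeks are the whole post-RT period in which section 2.3 expects added toxicity to show.

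The second primary objective is a safe nivolumab dose given with 60 Gy re-irradiation, and each level is judged on three patients. If 9.8 is followed, the SMC can discuss moving on, and inclusion can resume, when one of the three has been observed during RT but not after it. Section 9.8 itself foresees Grade 3 and 4 dermatitis and mucositis, so the end of RT and the weeks after it matter for this decision.

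**Working it through.** The check is calendar arithmetic from Cycle 1 Day 1 (week 0). The 8 weeks in 3.0 are counted from that day.

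**The plan's own anchor.** Section 5.2 and Table 1 give 60 Gy in 1.5 Gy fractions, twice daily, 5 days a week, in Cycles 2 and 3.

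- Fractions: 60 / 1.5 = 40. Treatment days: 40 / 2 = 20. Weeks: 20 / 5 = 4.
- RT starts at Cycle 2 Day 1 (week 2) and ends at week 2 + 4 = 6.
- Cycle 5 Day 1 is 4 cycles × 2 weeks = week 8, which is 8 − 6 = 2 weeks after RT. This reproduces the statement in 5.2 and matches the window in 2.3.

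The trigger in 9.8 is therefore week 6 of the third patient, and the trigger in 3.0 is week 8.

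**Effect of the stagger.** Starts within a level fall at weeks 0, 6 and 12. The earliest review is week 12 + 6 = 18 under 9.8 and week 12 + 8 = 20 under 3.0. Weeks since the end of RT are the review week minus the start week minus 6:

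| Patient | Start | 9.8 review, week 18 | 3.0 review, week 20 |
|---|---|---|---|
| 1 | 0 | 12 | 14 |
| 2 | 6 | 6 | 8 |
| 3 | 12 | 0 | 2 |

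Of the 3 × 2 = 6 patient-weeks in the post-RT window, 2 + 2 + 0 = 4 have been seen at week 18. From RT start to week 8, 6 + 6 + 4 = 16 of 18 have been seen. All of the missing time belongs to patient 3.

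**Who can start in the gap (weeks 18 to 20).**

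- After level 1: patient 4 could start 3.0 mg/kg at week 18. The stagger puts patient 5 at week 18 + 6 = 24. Patient 4's RT starts at week 18 + 2 = 20, when patient 3's window closes. The exposure inside the gap is one patient and one dose before RT.
- After level 2: 5.2 requires the stagger only during escalation. With no added patients, 20 − 6 = 14 places remain, and more than one of these patients could start in the gap.

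**Margin.** The 3.0 rule covers the window exactly. If RT starts 3 days late (the visit window in the flowchart), its nominal end is week 6.4, and week 8 is then only 1.6 weeks later. A count from the last fraction as well as from Cycle 1 Day 1 removes this dependence.

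**The case against.** The strongest reply is that the two rules can be reconciled. Section 3.0 states a minimum and 9.8 says the meeting comes after completion. Both are lower bounds, so a site that respects both reviews at week 8 of the third patient. That reading is available, and under it no window is missed. But 9.8 spells out what completion means, and 3.0 points to the dose-limiting toxicity section for its definitions. A reader may fairly take the shorter criterion as the governing one.

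The second reply is that the consequence is small, and this largely stands. The SMC discusses rather than clears automatically, and it may wait. A reader might infer more than the documents support in four ways:

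- *That a whole cohort starts at three times the dose inside the gap.* The 6-week stagger limits this to one patient after level 1.
- *That RT combined with the higher dose begins before patient 3's window closes.* The 2-week nivolumab lead-in puts patient 4's RT at week 20 at the earliest.
- *That a late event in patient 3 of level 1 would be lost.* During escalation the 9.8 rules apply at any dose level without a time limit. A possibly related Grade 3 event adds a patient at that level, and a Grade 4 event reduces the dose at once. After escalation, "the SMC will meet if two patients experience AE grade 3 or one patient experiences AE Grade 4, considered related to nivolumab".
- *That the plan also needs a minimum nivolumab exposure, an evaluability definition or a replacement rule.* Section 9.8 does define completion by RT alone. However, a patient who completes RT with little nivolumab is a scenario of unknown frequency, the SMC can weigh missed doses, and replacements would use up later places. The timing point does not depend on it.

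**Conclusion.** The inconsistency is real. As written, 9.8 permits the escalation review at week 18 of a level, with none of the third patient's 2-week post-RT window observed; 3.0 puts it at week 20, with all three windows complete. The size is one patient of three for 2 weeks. After level 1 this could expose at most one further patient to one pre-RT dose of 3.0 mg/kg; after level 2 it could affect more than one.

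This rests on three assumptions: the 8 weeks run from Cycle 1 Day 1, RT and cycles keep to schedule, and the SMC meets on the earliest day allowed. The documents give no toxicity rate for the combination and no distribution of onset times. The chance that the gap would change a dose decision therefore cannot be derived from them, and no such figure is claimed. It is a correction that should be made for safety and clarity, not a fault that invalidates the escalation design.

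**What to change.** In 9.8, replace the parenthesis that equates completing a dose level with completing RT by one based on 3.0, for example: *three patients have each reached at least 8 weeks from Cycle 1 Day 1 and at least 2 weeks after their last RT fraction*. Use the same definition in 3.0 and 5.2, and point their references to 8.8 at 9.8. State that inclusion stays on hold until the SMC has met on or after that point, for level 1 and level 2 alike. The Grade 3 and Grade 4 rules in 9.8 need no change.

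Cost: a few lines of text. If 9.8 is now followed, each level takes 20 weeks instead of 18, so 40 instead of 36 for both levels when no patients are added. If 3.0 is followed and RT runs to schedule, no time is added.
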